8.3.2 Parasitological assessment

Parasitological assessment will be done at baseline and at Day 30 (EOT), 3-month, 12-month and 24-month after treatment onset through microscopy examination of skin snip imprint smear sample and qPCR. In addition, skin sample will be collected from 20 subjects at the same time-points using non-invasive tape disc method (with the exception of 24 months), from where DNA will be extracted for qPCR. Results from the qPCR using skin snip sample will be compared with tape disc method.

The parasite load will be assessed by high power field (10x eyepiece and 100x objective). All slides will be coded and will be stored for reassessment.

The parasite load will be graded as follows:

Score	No. of parasites
0	0 parasites per 1000 fields
1+	1-10 parasites per 1000 fields
2+	1-10 parasites per 100 fields
3+	1-10 parasites per 10 fields
4+	1-10 parasites per field
5+	>10 parasites per field

8.4 Pharmacokinetics and Pharmacodynamics Assessments

8.4.1 Pharmacokinetic Assessments

PK assessment from the skin (biopsy) will be collected at the end of treatment i.e. at day 15 for patients allocated in the Ambisome[®] arm and day 22 for patients allocated in the Ambisome[®] + miltefosine arm. PK samples will be collected after administration of the drug dose. Adherence records, tissue weight of the samples, time of drug administration and time of PK samples collection have to be recorded systematically.

For patients allocated to Ambisome+miltefosine arm, miltefosine concentration will be measured in EDTA blood plasma collected at D8, D15, D22, D30 and 3 months visits. In addition, miltefosine concentration will be measured in the skin biopsy collected at D22 from patients allocated to combination arm.

For a sub-set of 30 patients per arm, total amphotericin B concentration will be measured in EDTA blood plasma collected at D1 (at the end of infusion, and at +2h, +4h, +8h, +22 hrs after the end of infusion), D15 (at prior to infusion, at the end of infusion and at +2h, +6h, +22hrs

after the end of infusion), and D22 (single sample for patients allocated to combination arm) or D30 (single sample for patients allocated to Ambisome monotherapy arm). In addition, total amphotericin B concentration will be measured in the skin biopsy collected at D15 from patients allocated in the Ambisome[®] monotherapy arm, and at D22 from patients allocated to combination arm.

As much as possible, a single blood draw should be performed per study visit to avoid multiple vein punctures. Sample for PK will be a 2mL EDTA whole blood sample/time point.

Samples will be stored on site in dark sample containers at minimally -20 ° C and regularly shipped minimally at -20° C conditions for analysis. Samples will be analysed for their amphotericn B and miltefosine content in plasma and skin following a procedure using liquid chromatography coupled to tandem mass spectrometry (LC-MS/MS) validated according to FDA and EMA guidelines. The development and validation of the miltefosine plasma assay has previously been published (T. P. Dorlo et al., 2008), validation documents concerning the amphotericin B plasma assay are on record.

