The Ambisome[®] will be given in 5 administrations over 2 ½ weeks to reduce safety risks. In addition, PD data from previous DNDi trials on VL have shown that parasite clearance is faster when Ambisome[®] was administered in multiple injections as compared to single administration. Although in this protocol we are not evaluating VL, but PKDL, splitting the dose over time may be beneficial for parasite dynamics, which will be monitored over time.

Miltefosine has a long half-life (> 6 days) and accumulates to eventually reach a steady state after 4 weeks of treatment. A minimum of 3-weeks treatment was considered necessary to reach sufficient exposure for the activity of miltefosine in PKDL patients. Still, this is a significant reduction as compared to the current 8-12 weeks of monotherapy regimen. If the proposed scheme shows to be safe and efficacious, it may be possible to consider regimens to treat PKDL which have shorter duration of treatment thus increasing compliance.

It has long been known that the underlying mechanism for controlling Leishmania infection and self-healing of dermal lesions is the cellular immune response, mediated by antigenspecific γ -interferon producing T-cells. Additional information to better understand the status and role of the host immune response and how it interacts when different treatment modalities are provided is needed. Similarly, studies to demonstrate that appropriate concentration of the drug is present in the right compartment, as well as to understand the drug to drug interaction and its correlation with the clinical outcome are crucial when optimizing a treatment modality. Lastly, data on parasite clearance during treatment of PKDL and follow-up may be correlated to immunological parameters and clinical outcome and thus may contribute to identify the best parameter to indicate cure in PKDL.

2 Study Objectives and Endpoints

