Vital signs and physical exam	х	х	х	Х	х	х	х	х	x	x	
Demographic data and Medical history	х										
Pregnancy test	х										
HIV test	x										
rK 39 test	х										
CBC, ALT / AST, Creatinine, Potassium, bilirubin	x		х	Х	х	x	Xp	x ^b	x ^b		
Skin snip for microscopy and qPCR	x					x	х		X	x	
Blood PD (qPCR)	х					х	х		х		
Tape disc skin sample for qPCR	х					х	х		Х		
Skin biopsy for PK				xc	Xa						
Plasma sample for Miltefosine PK ^a			х	Х	х	х	х				
Plasma sample for Ampho B		х		Х	х	x					
Blood sample for immunological parameters	х			Х		х	х		х		
PKDL evolution assessment, including photographs	х					х	х	х	х	x	
Ambisome monotherapy treatment			Amb injections: D1, D4, D8, D11, D15							1	
Ambisome + miltefosine treatment		Amb injections: D1, D4, D8, D11, D15 + Milt allometric D1-D21									
Safety assessment	SAEs and study related AEs		SAEs and AEs monito							nd AEs related to r procedures	

Protocol Version/Date: V3.0, 25 Feb 2020

a) Assessments to be performed only for the Ambisome® + Miltefosine arm

b) Only if abnormal at the previous assessment in a scheduled or unscheduled visit

c) Day 15 skin biopsy sample only for the Ambisome® monotherapy arm

d) A total of 30 subjects per arm will be included in the Ampho B PK assessment. Day 1 sampling to be performed at the end of infusion and at 2, 4, 8 and 22 hrs after the end of infusion. Day 15 sampling to be performed prior to infusion, at the end of infusion and at 2, 6 and 22 hrs after the end of infusion. One single sample to be collected at D22 for the Ambisome+miltefosine combination arm. One single sample to be collected at D30 for the Ambisome monotherapy arm. f. If the patient has completed 24 months /EOS before the approval of Protocol Amendment V3.0, 25 Feb 2020, the patient can be called as soon as possible for the final visit, this won't be considered a protocol deviation.

6 Enrolment procedures

A computer generated, randomization code will be used for patient treatment allocation to one of the two treatment arms. One set of individuals, opaque, sealed and sequentially numbered envelopes will be provided to the treatment sites, one envelope per patient. Eligible patients who fulfil all the inclusion criteria and have none of the exclusion criteria, and from whom informed consent has been obtained, will be randomized to one of the treatment regimens using the sealed envelopes.

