7.2 Doses and treatment regimens

Ambisome[®] monotherapy 5 x 4 mg/kg IV at D1, D4, D8, D11 and D15.

Combination of Ambisome[®] (5 x 4 mg/kg IV at D1, D4, D8, D11 and D15) plus miltefosine orally BID administration (allometric dosing) for 3 weeks.

Table 1 below describes the miltefosine regimen by an allometric scale, to be used for patients up to 30Kg.

Patients with weight > 30Kg, there is no difference between the allometric scale and conventional dose of 2.5mg/Kg/day. For these patients, the miltefosine regimen will be:

Patients > 30Kg and < 45Kg: 100mg of miltefosine per day, administered as 1 capsule of 50mg in the morning and 1 capsule of 50mg in the afternoon, with food, for 21 days.

Patients > 45Kg: 150mg of miltefosine per day, administered as 2 capsules of 50mg in the morning and 1 capsule of 50mg in the afternoon, with food, for 21 days.

An easy-to-use table (Table 2) with dosing scheme by weight and height will be provided to the investigators to define the exact daily miltefosine dose to be administered.

FEMALE									
HT (cm)	80-89	90-99	100-109	110-119	120-129	130-139	140-149	150-159	160
WT (kg)									
7									
8	30								
9	30			RISK	DF SE	/ERE N	ΛΑΙΝΙ	JTRITI	ON
10	30	40			REFER TO	THE WHO F	REFERENCE	CURVES	
11	40	40	40					0011120	
12	40	40	40						
13	40	40	40						
14	40	40	40	50					
15	40	40	50	50					
16	40	50	50	50					
17	40	50	50	50	50				
18	50	50	50	50	60				
19	50	50	50	60	60				
20	50	50	50	60	60	60			
21	50	50	60	60	60	60			
22	50	50	60	60	60	60			
23	50	50	60	60	60	70	70		
24	50	50	60	60	60	70	70		
25	50	60	60	60	70	70	70		
26	50	60	60	60	70	70	70	70	
27	50	60	60	70	70	70	70	80	
28	50	60	60	70	70	70		80	
29	50	60	60	70	70	70	80	80	00
30	50	60	60	70	70	80	80	80	80

Table 1 Daily allometric miltefosine dose for female and male children based on fat-free mass

Protocol Version/Date: V3.0, 25 Feb 2020

MALE									
HT (cm)	80-89	90-99	100-109	110-119	120-129	130-139	140-149	150-159	160
WT (kg)									
7									
8	40								
9	40			RISK	OF SEV	/FRF N	ΛΑΙ ΝΙ	JTRITI	ON
10	40	40				THE WHO F			•••
10	40 40	40 40			KLI LK IU		ALF LIVENCE	CORVES	
11	40 40								
12	50	50	50						
13	50	50	50						
15	50	50	60	60					
16	50	50	60	60					
17	50	60	60	60					
18	50	60	60	60	70				
19	50	60	60	70	70				
20	50	60	60	70	70				
21	60	60	60	70	70	70			
22	60	60	70	70	70	80			
23	60	60	70	70	80	80			
24	60	60	70	70	80		80		
25	60	60	70	70	80		80		
26	60	70	70	80	80		100		
27	60	70	70	80	80		100		
28	60	70	70	80	80		100	100	

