10.8 PK Analysis

For the pharmacokinetic data analysis, a population-based approach will be used employing non-linear mixed effects modelling (using NONMEM), to take into account within- and between-subject variability in all pharmacokinetic parameters, to optimally identify potential covariates such as body size descriptors (age, lean body mass, total body weight, etc) and other demographic parameters, but also interaction effects such as treatment-arm related differences in pharmacokinetics parameter estimates. Separate PK models will be developed for miltefosine in plasma and for total amphotericin B in plasma. The objective function value (equals -2 log-likelihood, derived from NONMEM) will be used to assess statistical significance of evaluated covariates and hierarchical structural models. The individual blood plasma:skin distribution ratio will be assessed based on the end of treatment samples. Exposure estimates in the skin that follow from the pharmacokinetic analysis will be compared to the IC90 values previously obtained for *L. donovani* parasites.

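### The only amphotericin B plasma sample later than 22 h after the last infusion is at D22 in one arm and D30 in the other, so a late-phase arm effect depends on the structural model

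*Protocol*

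**What the plan says.** Both arms receive the same Ambisome schedule, "5 x 4 mg/kg IV at D1, D4, D8, D11 and D15" (Section 7.2). Section 8.4.1 defines the amphotericin B subset: "For a sub-set of 30 patients per arm, total amphotericin B concentration will be measured in" EDTA plasma.

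The sampling times are the same in the synopsis, Section 8.4.1 and footnote d of the Section 5 schedule:

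- **D1, both arms:** "Day 1 sampling to be performed at the end of infusion and at 2, 4, 8 and 22 hrs after the end of infusion".
- **D15, both arms:** before infusion, at its end, and 2, 6 and 22 h later.
- **After that, one sample per patient:** "D22 (single sample for patients allocated to combination arm) or D30 (single sample for patients allocated to Ambisome monotherapy arm". Footnote d repeats this for the combination arm: "One single sample to be collected at D22 for the Ambisome+miltefosine combination arm".

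For miltefosine in the combination arm, Section 8.4.1 says "miltefosine concentration will be measured in EDTA blood plasma collected at D8, D15, D22, D30 and 3 months visits". D30 plasma therefore exists in both arms, but in the combination arm it is not assayed for amphotericin B.

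Section 10.8 plans separate population models for the two drugs, and lists among the effects to be identified "interaction effects such as treatment-arm related differences in pharmacokinetics parameter estimates". Section 1.5 calls it crucial to study drug levels in the right compartment "as well as to understand the drug to drug interaction and its correlation with the clinical outcome".

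**The concern.** Miltefosine is given in one arm only, so an arm effect on PK parameters can only concern amphotericin B. It is the one drug interaction that this trial can estimate against a concurrent randomised comparator.

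Beyond 22 h after the last infusion, knowing the arm means knowing the sampling time. An arm difference in the late phase is then read from the fitted curve and not from observations at a common time. If the model describes the slow phase poorly, the misfit at D22 in one arm and at D30 in the other can appear as an arm effect, or hide a real one. The sampling times are fixed in the protocol, and no later analysis plan can create a common late observation if the assay is never run.

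**Working it through.** The protocol states 30 patients per arm for this subset without a derivation and gives no amphotericin B PK values, so there is no figure to reproduce. All PK values below are assumptions.

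**1. Times after infusion** (days from Sections 5, 7.2, 8.1 and 8.4.1)

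- D15 pre-infusion sample, both arms: (15 − 11) × 24 = 96 h after the D11 infusion.
- Combination, D22: (22 − 15) × 24 = 168 h after the last infusion; 144 to 192 h if ±1 day is assumed.
- Monotherapy, D30: (30 − 15) × 24 = 360 h; 288 to 432 h with the stated ±3 days.
- 192 h is less than 288 h, so the windows do not overlap.
- Matched samples: 5 (D1) + 5 (D15) = 10 of 11 per patient.

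**2. Where the information on an arm effect lies**

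Model: two compartments, five infusions of an assumed 2 h, 30 patients per arm, residual SD 20%, between-subject SD 30% or 50%. Relative values are clearance 1, central volume 10, inter-compartmental clearance 1 and peripheral volume 20, 60 or 150, which give terminal half-lives of 32, 87 and 211 h. First-order information: I = Σ over arms of n J′V⁻¹J, with V = ω²GG′ + σ²I. J and G are the derivatives of log concentration with respect to the fixed and random effects. The standard error (SE) is the root of the diagonal of I⁻¹.

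| SE of log arm effect | as planned | no late sample | D30 added, D22 kept |
|---|---|---|---|
| Clearance, all settings | 0.079–0.131 | 0.079–0.134 | 0.079–0.130 |
| Peripheral volume, half-life 211 h, SD 30% | 0.129 | 0.236 | 0.098 |
| Peripheral volume, half-life 211 h, SD 50% | 0.166 | 0.275 | 0.143 |

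The clearance row is for an arm effect on clearance alone; the other rows are for effects on both parameters. Clearance hardly uses the late sample. The peripheral-volume effect does. There, adding D30 multiplies the information by (0.129/0.098)² = 1.73 or (0.166/0.143)² = 1.35. At a half-life of 32 h the late sample matters little: 0.083 as planned against 0.089 without it (SD 30%).

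**3. False arm effect when the slow phase is misspecified**

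Noise-free data from a three-phase profile, identical in both arms, were fitted with two compartments plus an arm effect. The true ratio is 1.00.

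*Effect on clearance.* Assumed half-lives are 6 h, 30 h and T, with coefficients 0.85 − f, 0.15 and f. Each cell gives the false ratio as planned → with D30 added and D22 kept.

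| T | f = 0.005 | f = 0.02 | f = 0.05 |
|---|---|---|---|
| 100 h | 1.065 → 1.031 | 1.044 → 1.021 | 1.030 → 1.012 |
| 200 h | 1.070 → 1.038 | 1.039 → 1.020 | 1.027 → 1.012 |
| 400 h | 1.067 → 1.038 | 1.038 → 1.020 | 1.030 → 1.013 |

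With identical times in both arms the ratio is 1.000 by construction.

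*Effect on peripheral volume.* Two further sets of assumed three-compartment profiles:

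- Four profiles: −29% in one, −7% in another, within about 5% in the other two. Adding D30 brought the first two to about 0%; the other two stayed within about 5%. The false clearance effect was 3% or less.
- Five profiles: ratios 0.45–0.61 as planned and 0.93–1.09 with D30 added and D22 kept. False clearance ratios fell from 1.04–1.33 to 1.02–1.07.

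The direction is consistent: D30 in both arms removes most of the false effect. The size depends heavily on the assumed profile.

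**The case against.** A reader might infer that the whole arm comparison of amphotericin B PK depends on the unmatched sample, or that this sample is the only view of elimination. The documents support neither reading. Ten of eleven samples match. One of them, before the D15 infusion, observes elimination about 96 h after the previous dose in both arms. Nor do unequal times alone bias a correctly specified population model. Comparing simple slopes from 22 h to the last sample would look alarming, but the protocol plans no such slope.

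Two further objections carry weight:

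- **Model comparison.** The protocol does not fix the number of compartments, and Section 10.8 compares structural models by objective function value. In a sweep of 64 assumed three-compartment profiles (30 per arm, residual SD 30%, no between-subject variability), every profile with a false volume effect of 20% or more had an expected objective-function penalty of at least 26 against the true structure. The planned comparison would therefore often expose the problem. Between-subject variability would weaken that signal, so the protection is partial.
- **Importance.** Drug interaction is not among the objectives or endpoints in Section 2. Section 3.1 calls the trial non-comparative, and Section 10.8 gives the arm effect as an example. The split also has an evident logistical reason: monotherapy has no D22 visit, and D22 is the day of the combination-arm skin biopsy.

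This limits the weight of the point. It does not remove the confounding in the late phase, and it gives no reason to leave the D30 plasma unassayed.

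**Conclusion.** The point holds for the late phase only. Beyond 22 h after the last infusion, arm and sampling time are fully confounded, and an arm effect on peripheral distribution, terminal elimination or late exposure depends on the structural model being right. Under misspecification the false effect falls mainly on peripheral volume, from negligible to a ratio of 0.45 across the assumed profiles. It is usually smaller on clearance: 1.03 to 1.07 over the nine profiles tabulated, and up to 1.33 in another set. These sizes rest on assumed PK values, noise-free fits and a model with one phase too few; a short terminal half-life or a successful model comparison would shrink them. The matter is a secondary PK one and does not affect the primary endpoint. It is worth correcting because the remedy is cheap.

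**What to change.** In the 30 combination-arm patients of the amphotericin B subset, also assay total amphotericin B in the D30 EDTA plasma already drawn for miltefosine. Keep D22 in the main model: it pairs with the skin biopsy, and in the checks above most of the false effect disappeared with D22 retained. Amend Section 8.4.1, the synopsis and footnote d to match.

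D30 sampling may already be complete. Footnote f of the schedule allows for patients who reached 24 months before version 3.0 was approved. If any had, and recruitment took at most 18 months (Section 3.2), the last patient entered at least 24 − 18 = 6 months before that approval. The remedy is then an assay of stored plasma.

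Cost: about 30 LC-MS/MS assays on top of 11 × 60 = 660 planned in the subset (30/660 = 4.5%), with no extra visit or blood draw. It is subject to enough plasma remaining: Section 8.4.1 gives a 2 mL whole-blood sample per time point and no residual volume. Both drugs are already due to be measured in this subset's plasma at D15 and D22, so a double assay at D30 follows existing practice.

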8.4.2 Pharmacodynamic Assessments

Blood samples for qPCR will be collected at baseline, Day 30 (EOT) and at 3 and 12 months follow up visits.

Skin snip samples for parasitological examination by microscopy and qPCR will be collected at baseline, D30 (EOT), 3 month, 12 month and 24-month follow-up.

Parasite load in blood and tissue aspirate: PD assessment will be based on real time quantitative polymerase chain reaction (qPCR) for *L. donovani* in EDTA blood or tissue aspirate, based on the amplification of kinetoplastid DNA (kDNA), to assess the parasite clearance over time during the treatment with miltefosine.

Approximately 1 mL EDTA whole blood will be immediately separated from blood EDTA samples taken for the qPCR analysis. qPCR will be performed according to SOP and standardised across the study sites. The qPCR will be performed at each respective hospital.

8.4.3 Immunological Assessment

Blood samples for immunological studies (3mL in heparin tube) will be collected at baseline, D15, D30 and at 3, and 12 months follow-up visits.

An aliquot of the whole blood (500 μ L) will be placed in 3 separate tubes: one containing 10 μ g/ml of soluble Leishmania antigen (SLA), one containing phytohaemagglutinin (PHA) as positive control, and one negative control; which will be subsequently incubated at 37°C for 24h. They are then centrifuged and supernatant is separated for analysis.

Cytokines IL-2, IFNY, TNFα, IL-10, and Granzyme B (and possibly other biomarkers after a preliminary screening) will be measured in the stimulated whole blood supernatant by BD[™] Cytometric Bead Array (CBA) Human Th1/Th2 Cytokine CBA. Lymphocyte subsets will be identified by FACS analysis.

Although whole blood assay with CBA and FACS would be the preferable method for cytokine analysis, ELISA reading of the whole blood supernatant will also be considered appropriate.

8.5 Assessment of Safety

Safety of the treatments will be assessed through routine monitoring of adverse events. At each study visit, the patients will be enquired about current adverse events or any events observed during the period previous to the visit. In addition, evaluation of hematology and blood chemistry parameters, regular measurement of vital signs and physical examinations will be made at D1, D8, D15, D22, D30 and each scheduled follow-up visit.

The frequency, severity, seriousness and causality assessments of AEs will be described, as well as frequency of SAEs or AEs that lead to treatment discontinuation.

Laboratory examinations

Hematology parameters CBC, WBC with differential and platelets will be analysed at screening, on days 8, 15, 22 (only for Ambisome[®] and miltefosine combination arm), and day 30 (EOT).

Biochemistry parameters creatinine, Potassium, AST, ALT and bilirubin will be analyzed at screening, on days 8, 15, 22 (only for Ambisome[®] and miltefosine combination arm), and day 30 (EOT).

Hematology and Biochemistry will be repeated at 3, 6 or 12-month follow-up visits only if abnormal at the previous assessment in a scheduled or unscheduled visit.

Samples will be analysed at the local laboratory using standardized equipment.

Approximately 4 mL of blood will be collected at each visit: 2mL in EDTA for the hematology and 2mL in dried tube for the biochemistry.

Lab parameters will be graded according to CTCAE v4.03 and abnormal values for clinical significance.

8.6 Adverse event definitions and reporting

8.6.1 Adverse Event definition

An adverse event will be defined as any untoward medical occurrence in a patient or clinical trial subject administered an investigational treatment and which does not necessarily have a causal relationship with this treatment.

It can therefore be any unfavourable and unintended sign (including an abnormal laboratory finding, for example), symptom, or disease temporally associated with the use of an investigational treatment, whether or not considered related to the investigational treatment.

Definition of an AE includes worsening (in severity and frequency) of pre-existing conditions/abnormalities ("Medical history") before first Investigational Medicinal Product (IMP) administration and abnormalities of procedures (i.e. ECG, X-ray...) or laboratory results which are assessed as "clinically significant" (see details in section 8.6.2).

What is not an AE?

Medical conditions present at the screening or initial study visit that do not worsen in severity or frequency during the study are NOT considered as AE.

Symptoms, exacerbation or worsening of the studied disease will NOT to be considered as AE nor captured on the AE page of the CRF if consistent with the anticipated natural progression

of the disease (overall and for this given subject).

Lack of efficacy of the IMP is NOT considered as AE.

